4.2.2 Reference Start Date and Analysis Day

For all randomized and treated subjects, the first treatment date will be the reference start date. For subjects randomized but not treated, the randomization date will be the reference start date. For subjects not randomized, the reference start date will be set to missing.

'Analysis Day' will be calculated relative to the reference start date (i.e., first treatment date or date of randomization), as Analysis Day = Assessment Date – First Treatment Date + 1 for randomized and treated subjects and as Analysis Day = Assessment Date - Randomization Date + 1 for subjects randomized but not treated.

4.2.3 Descriptive Statistics

Continuous data will be summarized in terms of the mean, standard deviation (SD), median, lower quartile, upper quartile, minimum, maximum and number of observations, unless otherwise stated. The minimum and maximum will be reported to the same number of decimal places as the raw data recorded in the database. The mean, median, lower quartile and upper quartile will be reported to one more decimal place than the raw data recorded in the database. The SD will be reported to two more decimal places than the raw data recorded in the database. In general, the maximum number of decimal places reported shall be four for any summary statistic.

Categorical data will be summarized in terms of the number of subjects providing data at the relevant time point (n), frequency counts and percentages.

Percentages will be presented to one decimal place. Percentages will not be presented for zero counts. Percentages will be calculated using n as the denominator. If sample sizes are small, the data displays will show the percentages, but any textual report will describe frequencies only.

Proportions will be reported as percentages (not as fraction of unit).

Changes from baseline in categorical data will be summarized using shift tables where appropriate.

4.2.4 Statistical Tests and Confidence Intervals

A two-sided type I error $\alpha = 0.05$ will be used to declare statistical significance for the primary endpoints and, when applicable, the secondary endpoints.

P-values greater than or equal to 0.0001, in general, will be presented to four decimal places. P-values less than 0.0001 will be presented as "<0.0001", P-values more than 0.9999 will be presented as ">0.9999".

The following flagging conventions will be applied for the p-values of all statistical testing:

- $0.01 \le p$ -values < 0.05 will be flagged with one asterisk (e.g. "0.0499 *")
- $0.001 \le p$ -value < 0.01 will be flagged with two asterisks (e.g. "0.0099 **")
- $0.0001 \le \text{p-value} < 0.001$ will be flagged with three asterisks (e.g. "0.0009 ***")
- p-value < 0.0001 will be flagged with four asterisks (e.g. "<0.0001 ****")

Confidence intervals (CIs) will be two-sided with 95% coverage for the primary endpoint and the secondary endpoints and will be presented to one more decimal place than the raw data.

4.2.5 Missing and Partial Dates Management

Start Date Imputation of Adverse Events:

- Imputation of adverse event end date has to be done before imputation of event start date.
- Completely missing: For subjects treated, impute to the first treatment date. For subject randomized but not treated, impute to the randomization date. For subjects not randomized, impute to the date of informed consent.
- Missing day and month: For subjects treated, impute to January 1st, unless year is the same as year of first treatment dose then impute to the first treatment date. For subject randomized but not treated, impute to January 1st, unless year is the same as year of randomization then impute to the randomization date. For subjects not randomized, impute to January 1st, unless year is the same as year of informed consent then impute to the informed consent date
- Missing day: For subjects treated, impute to the 1st of the month, unless month and year are the same as month and year of first treatment dose then impute to the first treatment date. For subject randomized but not treated, impute to the 1st of the month, unless month and year are the same as month and year of randomization then impute to the randomization date. For subjects not randomized, impute to the 1st of the month, unless month and year are the same as month and year of informed consent then impute to the informed consent date.
- If imputed event start date is after event end date (imputed or not), set the event start date to the imputed event end date.

Start Date Imputation of Prior/Concomitant Therapies and Medical/Surgical Procedures:

- Imputation of therapy/procedure end date has to be done before imputation of therapy/procedure start date.
- Completely missing: For subjects treated, impute to the first treatment date. For subject randomized but not treated, impute to the randomization date. For subjects not randomized, impute to the date of informed consent.
- Missing day and month: For subjects treated, impute to January 1st, unless year is the same as year of first treatment dose then impute to the first treatment date. For subject randomized but not treated, impute to January 1st, unless year is the same as year of randomization then impute to the randomization date. For subjects not randomized, impute to January 1st, unless year is

CCL

1.0

GALDERMA R&D RD.06.SPR.204245

the same as year of informed consent then impute to the informed consent date

- Missing day: For subjects treated, impute to the 1st of the month, unless month and year are • the same as month and year of first treatment dose then impute to the first treatment date. For subject randomized but not treated, impute to the 1st of the month, unless month and year are the same as month and year of randomization then impute to the randomization date. For subjects not randomized, impute to the 1st of the month, unless month and year are the same as month and year of informed consent then impute to the informed consent date.
- If imputed therapy/procedure start date is after therapy/procedure end date (imputed or not), • set the therapy/procedure start date to the imputed therapy/procedure end date.

Start Date Imputation of Medical History Diseases:

- Imputation of disease end date has to be done before imputation of disease start date. •
- Completely missing: Leave it missing. •
- Missing day and month: Impute to January 1st. •
- Missing day: Impute to the 1st of the month. •
- If imputed disease start date is after disease end date (imputed or not), set the disease start • date to the imputed disease end date.

End Date Imputation of Adverse Events, Prior/Concomitant Therapies and Medical/Surgical *Procedures. Medical History Diseases:*

- Completely missing and with outcome 'Not Recovered/Not Resolved' or 'Unknown' (Adverse • Events): Leave it missing.
- Completely missing and flagged as being ongoing (Prior/Concomitant Therapies and • Medical/Surgical Procedures, Medical History Diseases): Leave it missing.
- Completely missing and with an outcome different from 'Not Recovered/Not Resolved' and ٠ 'Unknown' (Adverse Events): Impute to the last contact date.
- Completely missing and not flagged as being ongoing (Prior/Concomitant Therapies and ٠ Medical/Surgical Procedures, Medical History Diseases): Impute to the last contact date.
- Missing day and month: Impute to December 31st, unless year is the same as last contact date • then impute to the last contact date.
- Missing day: Impute to the last day of the month, unless year and month are the same as year • and month of last contact date then impute to the last contact date.

4.2.6 **Analysis Visits**

Efficacy, safety and subject reported outcomes by-visit summaries and analyses will use analysis visits. Both scheduled and unscheduled visits (including early termination visit) will be windowed based on the following analysis visit windows.

Analysis Visit	Target Study Day	Analysis Visit Window
Baseline	1	<= 1
Week 1	8	4 - 11

Analysis Visit	Target Study Day	Analysis Visit Window				
Week 2	15	12 - 19				
Week 4	29	22 - 36				
Week 8	57	50 - 64				
Week 12	85	75 - 95				
Week 16	113	103 - 123				
Week 20	141	131 - 151				
Week 24	169	>= 159				

If two or more assessments (include both scheduled and unscheduled assessments) are available for any analysis visits, then all assessments will be listed and the following rules will be applied for determining the values to be used for the summaries and analyses.

- Efficacy assessments, excluding colorimetry data: the assessment taken closest to the target study day will be used for the summaries and analyses. If there are multiple assessments with same difference from target day, the latest assessment will be used for the summaries and analyses;
- Safety assessments, excluding clinical laboratory tests: the assessment taken closest to the target study day will be used for the summaries and analyses. If there are multiple assessments with same difference from target day, the latest assessment will be used for the summaries and analyses;
- Clinical laboratory tests: the latest assessment will be used for the summaries and analyses;
- Subject Reported Outcome: the assessment taken closest to the target study day will be used for the summaries and analyses. If there are multiple assessments with same difference from target day, the latest assessment will be used for the summaries and analyses;
- Colorimetry data: data derived from the latest photograph will be used for the summaries and analyses.

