**Study Schema** 

#### 5.1.1 Schedule of Assessments

## 5.1.1.1 Study Assessment Considerations Pertaining to the COVID-19 Pandemic

Subjects who are wearing a face mask should continue to do so until seated in an exam room, in accordance with your local guidelines. The general sequence of examinations should begin with a wellness assessment, review of dosing calendar/compliance and completion of subject questionnaires prior to performing acne assessments (IGA, lesion counts), local tolerability assessment and imaging.

The following study procedures are permitted, within the protocol defined visit windows, to ensure safety of enrolled subjects and continuity of the follow-up visit schedule, due to circumstances when a subject is unable to return to the clinic due to the COVID-19 pandemic. These circumstances include, but are not limited to, shelter in place guidelines, quarantines, travel restrictions, clinical site closures, etc. As with all study procedures, clear and complete documentation in source records is required in these circumstances.

- Remote Visits (phone, etc) in lieu of scheduled office visits
  - o for safety and wellness assessment (concomitant medications, AEs, etc)
- Questionnaire completion
  - o sent to subject by email or mail
  - o subject signs, dates and returns, by email of mail.
- Collection of previously dispensed study drugs and dosing calendar, from an adult family member
  - Weighing of returned topical study drug is required
  - A follow-up phone call with the subject is required to review the dosing calendar and returned study drugs, for appropriate clarification in study medication use.

- Dispensing of new study drugs and non-investigational supplies (a new dosing calendar, non-IP supplies, etc) to an adult family member
  - Weighing of topical study drug is required, before dispensing
  - A follow-up phone call with the subject is required to convey reminders on proper instructions for study medication and other supplies use, and to use the newly dispensed study drugs beginning that evening (and to stop using previously dispensed medication, if not returned).

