- FDA COVID-19 guidance allows for secure delivery for self-administered study medication. In cases where a family member is not available for dispensing study medication and other supplies, delivery using an express courier with appropriate temperature control capability is permitted. A follow-up phone call is required in these circumstances to confirm receipt and provide the subject with appropriate reminders and proper instructions for study medication and other supply use.

Note: The decision to dispense additional study drug should be based on the investigator's clinical judgement that ongoing dosing does not pose undue safety risks to the subject, and that the subject is willing to continue using the study drug. In all cases for maintaining study drug availability to subjects, existing requirements for maintaining study drug supply accountability remain.

Subjects must be present in the office for the following assessments:

- PIH assessments (ODS, CCI
- •
- •

GALDERMA R&D RD.06.SPR.204245 V00 18AUG2021 Page 29 of 104

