# 5.1.1.2 Study Assessment Schedule

	CLINICAL TRIAL VISITS									
	Visit 1	Visit 2	Visit 3	Visit 4	Visit 5	Visit 6	Visit 7	Visit 8	Visit 9	Visit 10
PROCEDURES	Screening (Up to 28 days prior to Baseline)	Baseline	Week 1 (±1 d)	Week 2 (±1 d)	Week 4 (±3 d)	Week 8 (±3 d)	Week 12 (±3 d)	Week 16 (±3 d)	Week 20 (±3 d)	Week 24 (±5 d) or ET
Informed consent/Photography Consent	X									
Inclusion/Exclusion Criteria	X	X								
Demographics/ Relevant medical history/ Prior therapies a	X									
Urine Pregnancy test (UPT) b	X	X			X	X	X	X	X	X
Efficacy Assessments										
Overall Disease Severity PIH Score assessed by the investigator	X	X					X	X	X	X

GALDERMA R&D RD.06.SPR.204245 V00 18AUG2021 Page 30 of 104

	CLINICAL TRIAL VISITS									
	Visit 1	Visit 2	Visit 3	Visit 4	Visit 5	Visit 6	Visit 7	Visit 8	Visit 9	Visit 10
	Screening (Up to 28 days prior to Baseline)	Baseline	Week 1 (±1 d)	Week 2 (±1 d)	Week 4 (±3 d)	Week 8 (±3 d)	Week 12 (±3 d)	Week 16 (±3 d)	Week 20 (±3 d)	Week 24 (±5 d) or ET
Safety Assessments										
Local tolerability assessment of face		X	X	X	X	X	X	X	X	X
Adverse events c	X	X	X	X	X	X	X	X	X	X
Concomitant therapies	X	X	X	X	X	X	X	X	X	X
	Investigational Product Administration									
Dispensation of investigational products and subject diary		X			X	X	X	X	X	
Dispensation of non-investigational products		X			X	X	X	X	X	

GALDERMA R&D RD.06.SPR.204245 V00 18AUG2021 Page 31 of 104

	CLINICAL TRIAL VISITS									
	Visit 1	Visit 2	Visit 3	Visit 4	Visit 5	Visit 6	Visit 7	Visit 8	Visit 9	Visit 10
PROCEDURES	Screening (Up to 28 days prior to Baseline)	Baseline	Week 1 (±1 d)	Week 2 (±1 d)	Week 4 (±3 d)	Week 8 (±3 d)	Week 12 (±3 d)	Week 16 (±3 d)	Week 20 (±3 d)	Week 24 (±5 d) or ET
Return of investigational products and accountability					X	X	X	X	X	X
Subject Diary/Compliance d			X	X	X	X	X	X	X	X
Exit form										X

- a. Only prior therapies that were stopped within 6 months of the Baseline visit and that may have an impact on inclusion/exclusion criteria should be recorded. Treatment that continues after Baseline should be recorded on the Concomitant Treatment Form of the CRF.
- b. For Subject of childbearing potential: UPT should be conducted if no menstrual period in the preceding four weeks. Urine Pregnancy Tests are mandatory at Baseline and at Week 24 / ET (early termination).
- c. Adverse event onsets after subject signature of the informed consent form should be recorded on the AE Form of the CRF.

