### 5.5.2 Unscheduled Visit

The subject should be reminded to adhere to the study visit schedule. Unscheduled visits are unplanned and may include examinations for safety or repeat study assessments. Visits occurring outside of the visit window are not considered unscheduled visits.

Assessments to be conducted at the unscheduled visit will depend on the reason for the visit: Any of the procedures/assessments listed in Section 5.1.1.2 Schedule of Assessments may be conducted, as appropriate.

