4.10.1.3 Handling of Dropouts or Missing Data

Distinct missing data patterns of PIH Overall Disease Severity scores, total lesion counts, inflammatory lesion counts, non-inflammatory lesion counts and Investigator Global Assessment (IGA) scores with their corresponding number and percentage of subjects will be presented in order to establish whether they are monotone or non-monotone.

CCI

GALDERMA R&D RD.06.SPR.204245

The primary method of imputation for missing data of primary and secondary efficacy endpoints will be Multiple Imputation (MI) under the Missing At Random (MAR) assumption.

For the primary MAR based multiple imputation, the MI procedure of the SAS system will be used to generate sets of data with missing values imputed from observed data. It is expected that the pattern of missing data will be monotonic, with slight deviations being corrected by the Markov Chain Monte Carlo (MCMC) method of the MI procedure.

The following steps will be followed:

1. For PIH Overall Disease Severity scores, CCI

. If the pattern is not monotone, the MCMC method of SAS PROC MI will be used to make it monotone. The single chain method will be used, with 200 burn-in iterations and 100 iterations between imputations. In case of lack of convergence with the single chain method, the multiple chain method will be used. Separate imputations by treatment group will be carried out. The minimum values for imputed variables will be set to 0, in order to force PROC MI to redraw another value for imputation when an intended imputed value is less than the 0. For PIH Overall Disease Severity scores only, the maximum value for imputed variables will be set to 8, in order to force PROC MI to redraw another value for imputation when an intended imputed value is greater than the 8.

Imputed values will be rounded to the nearest integer. The seed number will be set to 204245 and fifty (50) imputations will be created.

- 2. SAS PROC MI will be used for imputing missing values of data with monotone missing pattern. If the MCMC method of step 1 was previously employed, one imputation will be made using each of the fifty (50) MCMC-imputed datasets. If the MCMC method of step 1 was not previously employed, fifty (50) imputations will be created assuming the data are Missing At Random. The seed number will be set to 204245. These imputations will use the following models:

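### The SAP's analysis windows assign Days 96–102, 124–130 and 152–158 to no visit, so a real ODS score from an off-schedule or early termination visit can go unused

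*SAP*

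**What the plan says.** SAP 4.2.6 (Analysis Visits) makes study day, not visit label, decide where a score counts: "Efficacy, safety and subject reported outcomes by-visit summaries and analyses will use analysis visits". It then adds: "Both scheduled and unscheduled visits (including early termination visit) will be windowed based on the following analysis visit windows". For the visits at which ODS is scored after baseline, the table gives:

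| Analysis visit | Target day | Window |
|---|---|---|
| Week 12 | 85 | 75–95 |
| Week 16 | 113 | 103–123 |
| Week 20 | 141 | 131–151 |
| Week 24 | 169 | 159 or later |

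Where several scores share a window, the SAP has a rule: "Efficacy assessments, excluding colorimetry data: the assessment taken closest to the target study day will be used for the summaries and analyses". It has no rule for a score that falls between windows.

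SAP 4.10.1.3 covers absent values: "The primary method of imputation for missing data of primary and secondary efficacy endpoints will be Multiple Imputation (MI) under the Missing At Random (MAR)". Its ODS imputation model uses non-missing scores from earlier scheduled time points, including baseline.

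In the protocol, the schedule (5.1.1.2) allows ±3 days at Weeks 12, 16 and 20. It heads the last column "Week 24 (±5 d) or ET", and ODS is scored at that visit. Section 5.5.2 says of late or early attendance: "Visits occurring outside of the visit window are not considered unscheduled visits". Section 5.1.1.1 rules out remote ODS scoring: "Subjects must be present in the office for the following assessments".

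**The concern.** A score on one of the unassigned days is a genuine in-clinic rating on the primary scale. Because every by-visit efficacy analysis goes through the windows, that rating has no slot. The visit it might have filled is then treated as missing and imputed. The observed-case analysis, which is meant to use the data as collected, loses the rating too, and the imputation model cannot condition on it.

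ET visits are the most exposed. Their timing follows the day a subject leaves, not the calendar, and these are the subjects whose Week 24 value the imputation has to supply. Losing their most recent rating removes it both as an outcome and as a predictor. The per-protocol set (SAP 4.6) also requires a Week 24 assessment, so window assignment can decide membership of that set.

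**Working it through.** **1. Gaps.** Each gap runs from the upper bound of one window plus 1 to the lower bound of the next minus 1.

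| Between | Unassigned days | Days after earlier target | Days before next target |
|---|---|---|---|
| Weeks 12 and 16 | 96–102 | 11–17 | 11–17 |
| Weeks 16 and 20 | 124–130 | 11–17 | 11–17 |
| Weeks 20 and 24 | 152–158 | 11–17 | 11–17 |

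That is 3 × 7 = 21 of the 158 − 75 + 1 = 84 days from Day 75 to Day 158, or 25% of days. (The table has other gaps before Day 75, but no ODS visit is scheduled between baseline and Week 12.)

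**2. Who can reach a gap.** Protocol windows around the same targets are Days 82–88, 110–116, 138–144 and 164–174 (taking first application as the day of the baseline visit). None touches a gap. Only out-of-window, unscheduled and ET visits can fall there.

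**3. What is lost.** SAP 4.10.1.4 lists seven ordered secondary tests; six of them (absolute and percent change at Weeks 20, 16 and 12) use the three intermediate visits. A last score on Days 155–158 is 169 − 158 = 11 to 169 − 155 = 14 days before target, and Week 24 is imputed in its place. A last score on Days 152–154 is 15–17 days before the Week 24 target and 11–13 days after the Week 20 target, and serves neither visit.

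**4. Size.** The documents give no distribution of visit or dropout times, so the count cannot be computed. As an illustration only, start from the planned dropout. The plan's own figure reproduces: 2 × (1.960 + 1.282)² × 1.4² / 1.0² = 41.2, rounded up to 42 per arm; 42 / (1 − 0.30) = 60 per arm, 120 in total. Planned dropouts are 0.30 × 120 = 36. Assume that all attend an ET visit, that 25% to 75% of them leave on Days 75–158, and that their days are spread evenly:

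- Low: 36 × 0.25 × 0.25 = 2.25
- High: 36 × 0.75 × 0.25 = 6.75

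So roughly 2 to 7 subjects would have an ET score in a gap under those assumptions.

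**5. What contiguous windows recover.** Midpoints between targets are (85 + 113)/2 = 99, (113 + 141)/2 = 127 and (141 + 169)/2 = 155. With tie days given to the later visit, the windows are 75–98, 99–126, 127–154 and 155 or later. Days 75–158 are then fully covered: 24 + 28 + 28 + 4 = 84. The greatest distance from target at the new boundaries is 14 days (Days 99, 127 and 155).

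- A visit 11–13 days late (3 of the 7 gap days) returns to its intended visit.
- A visit 14–17 days late (4 of 7) counts toward the next visit, and only if nothing closer to that target exists.
- An ET score that follows an on-time visit is used on 4 of the 7 days. On the other three, the on-time score is closer to target and is kept. In the illustration, 2.25 × 4/7 = 1.3 to 6.75 × 4/7 = 3.9, so about 1 to 4 subjects.

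**The case against.** The strongest reply is that the gaps are remote. The SAP already allows ±10 days at Weeks 12–20, more than three times the protocol's ±3, and no visit inside protocol windows is affected. That stands, and it limits the point to off-schedule and ET visits. The 25% figure is a share of days; a reader might take it for a share of scores, but visits cluster at their targets.

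A reader might infer that the protocol expects late in-clinic ODS visits because it names "shelter in place guidelines, quarantines, travel restrictions, clinical site closures, etc". It does not go that far. Section 5.1.1.1 allows substitute procedures, mainly remote contact, inside the visit windows, and a remote visit yields no ODS score. Nor do the documents support any assumed rate of late visits.

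A reader might also infer that the open end of the Week 24 window contaminates the primary endpoint. The documents do not support that as a defect. No visit is planned after Week 24, the closest-to-target rule already prefers an on-time score, and Protocol 5.3.4 asks subjects who stop drug to stay so that primary-endpoint data are collected. A hard cap would itself replace observed scores with imputed ones.

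Two further objections have some force. The SAP does not say in words that a between-window score is dropped; this follows from 4.2.6, and whether last observation carried forward may use such a score is left open. SAP 4.10.2.1 adds early termination in parentheses after Week 24, which might suggest that an ET score counts as Week 24 on any day; but 4.2.6 expressly windows ET visits by study day, so the two need to be read together.

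Finally, contiguous windows do not send every late score back to its own visit, and a Week 20 visit 14–17 days late becomes the Week 24 value if no later score exists. Both are true and should be stated in the SAP.

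**Conclusion.** The concern holds in a limited form. The window table leaves 21 days unassigned, and no other section of either document says how an ODS score on those days is used. The direct effect is on the six Week 12–20 secondary tests and on the imputation for dropouts. It reaches the primary endpoint directly only when a subject's last score falls on Days 152–158.

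The number of subjects cannot be computed from the documents; the range of about 2 to 7 rests wholly on the stated assumptions about ET attendance and timing. The conclusion rests on one inference, that a score assigned to no analysis visit enters no by-visit analysis. This is a cheap improvement that uses more of the observed data. It does not show that the primary result would be biased.

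**What to change.** Before unblinding, amend the SAP 4.2.6 table for ODS so that the windows meet at the midpoints, and state which side takes the tie days. One version: Week 12 = Days 75–98, Week 16 = 99–126, Week 20 = 127–154, Week 24 = 155 or later. Keep the closest-to-target rule. Say plainly that scores 14–17 days late count toward the next visit only if nothing closer exists, and align the ET wording in 4.10.2.1 with the table.

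Keep late Week 24 scores in the primary analysis. Add one sensitivity run that treats ODS scores far beyond target as missing, for example after Day 183 (169 + 14).

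The cost is one table, a few sentences and one extra run, with no new data and no change to the planned sample size. SAP 4.14 already allows updates arising from blind review. The downside is that some scores up to 14 days from target will be used.
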